6.1. Enrollment and Training

Potential study participants (usually the primary care provider for minor children) will be contacted by a member of the clinical research site staff via text, email, or phone call who will direct them to the link to the study HEROS home web page. If interested in participating in the study, the participant/caregiver will be given instructions to view the study web portal. The potential participant will read an information sheet that includes details about the study, study requirements, and study risks, and will provide assurance that each participating family member has read the information sheet and agrees to participate for themselves, index participants, and other family members. The participant will then be directed to complete an electronic registration form and to complete a baseline questionnaire. Once this process is completed, the participant is considered enrolled in the study and will be assigned a unique participant number. All participating family members will be assigned unique participant numbers. Upon completion of these tasks, the sample kit distribution center will mail each household a set of sample collection kits for initiation of bio-sampling.

Once enrolled, the primary contact/caregiver and each participant will be requested to undergo a web-based training that will describe in detail the processes of sample collection and handling. Study staff will be available by phone, Skype, text, or video conferencing for further instructions and clarifications on sample collection procedures.

At Week 18, the primary contact/caregiver will be electronically sent an information sheet that includes details about a study extension that will include collecting 4 additional nasal swabs for a total of 14 nasal swabs over 28 weeks. The information sheet will require that each participating family member attest that they have read the information sheet. The household will have the option to continue with the original visit and sample collection schedule (10 nasal swab collections over 24 weeks), to participate in the study extension with 4 additional nasal swab collections, or to request further information via contact with their local study site.

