6.2. Index participants and Household Contacts Study Assessments

6.2.1 Caregiver-Collected Samples

At the times shown in the Schedule of Events (Table A), the primary contact/caregiver will collect nasal swabs from the index participants and all family members that are enrolled in the study at the beginning of the study (Week 2) and every 2 weeks thereafter for 9 collections, then a final 10th nasal swab collected at the end of the study (total 10 nasal swabs collected over 24 weeks). If the household agrees to participate in the study extension, 4 additional nasal swabs will be collected between Week 18 and Week 28 (Table A). Stool samples via swabs will be collected from the index participants and all family members that are enrolled (starting at Week 2) into the study (Table A). Blood samples will be collected via the OnDemand device from the index participants and all family members that are enrolled in the study and 2 years of age and older (Table A). Nasal secretion and/or saliva samples may also be collected from the index participants and all enrolled family members at Week 24. Samples will be shipped as instructed in the sample kit package. Details of the nasal swab, stool collection, blood collection, nasal secretion, and saliva procedures will be provided in the sample kit package.

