6.4. Sample Collection/Questionnaire Completion Windows

Sample collection and completion of the study questionnaires should take place within the time limits specified in the Schedule of Events (Table A).

Table A. Schedule of Events for All Participants

*The window for sample collection and completion of Symptom and Exposure surveys is (+/-) 4 business days

¹There is no window for the baseline (Week 2) blood collection.

²Additional nasal swab and a stool samples will be collected when a household member shows signs of a viral illness and a study-specified threshold for symptom algorithm has been met. For the first illness, the nasal swab sample will be collected within 24 hours from all study participants, including the affected household member, and a stool sample from just the affected household member. Subsequent illnesses will be assessed only if the index participant is affected; in this case a swab and a stool sample will be obtained within 24 hours only from the index participant.

³A nasal secretion and/or saliva sample may be collected at End of Study.

⁴Nasal swabs will be collected at Week 20, 22, 26 and 28 and Health Check Surveys at Week 19, 21, 23, 25, and 27 from participants that agree to participate in the study extension.

⁵An end of study blood sample will be collected from all study participants that are at least 2 years old at Week 24 or at Week 28, if the participant decided to continue in the study with the original visit plan or agreed to participate in the extension, respectively.

⁶An additional blood sample will be collected from all study participants that are at least 2 years old three weeks after a first illness in the household and a study-specified threshold for the symptom algorithm has been met.

7. Laboratory Assays

- SARS-CoV-2 detection and nasal transcriptomics. RNA extracted from all swabs will be used to perform RT-qPCR for SARS-CoV-2. The remaining RNA and DNA will be stored for possible detection (and quantification) of other respiratory viruses, for generating the host transcriptome response to infection (from airway epithelial and any immune cells that were present on the nasal swab), and for delineating the nasal microbiome at the time the swab was collected.

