11.2 Analysis Plan

Population description

Baseline characteristics of 2000 index children and their families that include age, sex, household members, co-morbidities, proportion with evidence of SARS-CoV-2 infection at baseline, and follow-up will be described using standard statistical techniques such as proportions for categorical variables and means and standard deviations (SD), or medians and interquartile ranges as appropriate.

Primary outcome: The cumulative incidence of SARS-CoV-2 RNA detection in nasal samples among index participants and their household contacts over the study period

Time to event analyses will be conducted among participants that are SARS-CoV-2 serologically negative at entry. We will use Kaplan-Meier cumulative morbidity curves for the primary analysis. The primary endpoint will be calculated at the end of follow-up or fate defined as follows. Follow-up time will be the time from entry until the first of the following events:

- Tests positive for SARS-CoV-2 RNA in nasal samples
- Is lost to follow-up or withdraws from the study
- End of study (24 weeks)

Fate at the end of follow-up will be:

- 1 (positive): if the patient tests positive for SARS-CoV-2.
- 0 (censored): if the patient has no evidence of having had disease by the end of follow-up.

Attack rates

SARS-CoV-2 attack rate per person-week will be calculated. Attack rates within families will also be estimated.

Secondary outcome: time to the index participants and their household members with detectable SARS-CoV-2-specific antibodies in serum over the study period.

Cox regression on seroconversion status at 24 weeks: Hazard ratios will be modeled using Cox Regression to compare demographic and clinical factors to the time to detectable SARS-CoV-2-specific antibodies in serum.

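### Entry is undefined for the primary analysis, and seronegative participants who are RNA-positive at the first swab count as incident cases

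*Combined protocol and SAP*

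**What the plan says.** Section 11.2 defines the follow-up clock: "Follow-up time will be the time from entry until the first of the following events". The events are a positive nasal RNA test, loss or withdrawal, and end of study at 24 weeks. Entry is not defined there or elsewhere.

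The analysis set is restricted by serology alone: "Time to event analyses will be conducted among participants that are SARS-CoV-2 serologically negative at entry". Section 11.2 makes no exception for the first swab. It plans to describe the "proportion with evidence of SARS-CoV-2 infection at baseline", but has no rule that keeps those people out of the incident count.

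Two starting points are available:

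- **Registration.** After the registration form and baseline questionnaire, Section 6.1 says: "Once this process is completed, the participant is considered enrolled in the study". Sampling follows later: "Upon completion of these tasks, the sample kit distribution center will mail each household a set of sample collection kits". The synopsis also counts study duration from enrolment.
- **Week 2.** Section 6.2.1 schedules nasal swabs "at the beginning of the study (Week 2) and every 2 weeks thereafter for 9 collections". Footnote 1 to Table A calls the Week 2 blood the baseline sample and gives it no window.

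For the swabs, Section 6.4 says: "The window for sample collection and completion of Symptom and Exposure surveys is (+/-) 4 business days". Section 3.1 limits blood collection to participants aged 2 years and older.

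**The concern.** A cumulative incidence needs a time zero at which everyone counted is free of the event. Here the event is RNA detection, but the filter at entry is antibody. Someone who is RNA-positive and still seronegative passes the filter and becomes an event at the first swab.

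- **If entry is Week 2**, that person is positive at time zero, which is prevalence counted as incidence.
- **If entry is registration**, infections acquired before registration and still detectable at Week 2 are counted as incident. In the other direction, a participant infected after registration who has seroconverted by the Week 2 draw is dropped as positive at entry, although the infection was incident. The at-risk set is then fixed by information collected about two weeks after the clock starts.

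At stake are the primary cumulative incidence, through its numerator and its analysis set, and the attack rate per person-week, through its denominator.

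**Working it through.** **Inputs from the documents.** Swabs at Weeks 2, 4, ..., 18 and 24 on the original schedule (Section 6.2.1); 24-week horizon (Section 11.2); 2000 families (Section 11.3).

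**Assumed, because the documents do not give them.** Nasal RNA detectable for D = 14, 21 or 28 days, with d = D/7 weeks. Incidence proportional to exp(-g t), with g = 0 (flat), ln2/4 (halving every 4 weeks) or -ln2/4 (doubling every 4 weeks). No removal by serology.

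**1. The plan's own figures.** Wilson 95% intervals with n = 2000 are 2.34-3.84% at 3%, 4.13-6.04% at 5%, 8.76-11.39% at 10% and 18.31-21.81% at 20%. They agree with Section 11.3 to within 0.1 point and do not depend on time zero.

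**2. Effect of the lead-in alone.** If entry is registration, 2/24 = 8.3% of nominal person-time precedes the first scheduled swab. With the same events, the person-week rate from registration is 22/24 = 0.917 of the rate from the first swab, about 8% lower (24/22 = 1.09 the other way). The Kaplan-Meier end value does not move: a common two-week shift leaves the risk set and event count at each swab as they were. One simulated data set (2000 people, 0.5% positivity per swab, 10% drop-out) gave 4.49% from either origin.

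**3. Share of events at the first swab.** Integrate incidence over these intervals:

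- first-swab events: [2-d, 2]
- the part infected before registration: [2-d, 0]
- later events: [2, 18] plus [24-d, 24]

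| Incidence | D | First swab | Before registration | Weeks 2-18 | Last swab | Total | First-swab share | Pre-registration share |
|---|---|---|---|---|---|---|---|---|
| Flat | 14 | 2 | 0 | 16 | 2 | 20 | 10.0% | 0% |
| Flat | 21 | 3 | 1 | 16 | 3 | 22 | 13.6% | 4.5% |
| Flat | 28 | 4 | 2 | 16 | 4 | 24 | 16.7% | 8.3% |
| Halving | 14 | 1.69 | 0 | 3.83 | 0.04 | 5.55 | 30% | 0% |
| Halving | 21 | 2.78 | 1.09 | 3.83 | 0.06 | 6.67 | 42% | 16% |
| Halving | 28 | 4.08 | 2.39 | 3.83 | 0.09 | 8.00 | 51% | 30% |
| Doubling | 14 | 2.39 | 0 | 122.4 | 108.2 | 233.0 | 1.0% | 0% |
| Doubling | 21 | 3.31 | 0.92 | 122.4 | 149.7 | 275.4 | 1.2% | 0.3% |
| Doubling | 28 | 4.08 | 1.69 | 122.4 | 184.7 | 311.2 | 1.3% | 0.5% |

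If entry is Week 2, the whole first-swab share is prevalent. If entry is registration, only the last column is.

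**4. On the scale of the endpoint.** Take a true 24-week risk of 5% with constant hazard: -ln(0.95)/24 = 0.00214 per week. Cumulative incidence is 1 - exp(-0.00214 x w), where w is the number of weeks of infection the swabs can detect.

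- D = 14: w = 20 with first-swab positives, 18 without. Cumulative incidence 4.18% against 3.77%.
- D = 28: w = 24 against 20. Cumulative incidence 5.00% against 4.18%.

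The shift is 0.4 to 0.8 points. The Wilson half-width at 5% is (6.04 - 4.13)/2 = 0.96 points. Per 2000 people, first-swab positives number 8.5, 12.8 and 17.0 for the three values of D. Of these, 0, 4.3 and 8.5 were infected before registration.

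**The case against.** **Entry may not mean registration.** This stands. Registration is the likelier reading, because duration is counted from enrolment and the 24-week end matches the last original visit. It remains an inference. On the Week 2 reading the lead-in and the late at-risk set largely disappear, but the first-swab positives are then plainly prevalent.

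**Untested time does not reach the primary estimate.** This also stands. A reader might infer that the lead-in biases the Kaplan-Meier result, and step 2 shows that it does not. Nor is the lead-in strictly unobserved: if RNA lasts at least 14 days, the Week 2 swab looks back over it. The first swab may also come before Week 2, given its window and the possibility of an illness swab.

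**First-swab positives are not all contamination.** Correct under the registration reading. At D = 14 none predates registration, so the 10-17% must not be read as a bias figure. The 30% pre-registration share is one corner of the assumptions (28 days, halving incidence, no serologic removal). Pre-registration infections are at least two weeks old at the Week 2 draw, so serology would remove some. The documents do not allow the net of this and the wrongly dropped seroconverters to be computed.

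**Late blood.** A reader might take the absence of a window to mean that blood can be drawn at any time. It can equally mean no tolerance, and needs clarifying.

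**The endpoint is RNA detection, not onset.** Counting a detection at the first swab fits that wording. But the primary objective is the incidence of infection, and the seronegative restriction shows that a cohort at risk is intended.

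**The fix can land further from the truth.** In the flat model the detected share of the true rate is 20/24, 22/24 and 24/24 (0.83, 0.92, 1.00) as planned, and 18/22, 19/22 and 20/22 (0.82, 0.86, 0.91) after the fix. The arithmetic is right. The shortfall comes from the gap between the Week 18 and Week 24 swabs, which prevalent cases happen to offset. That is not a reason to keep them.

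**Conclusion.** The concern holds in limited form and should be settled before the analysis. Entry is undefined, and the stated rules count seronegative participants who are RNA-positive at the first swab as incident on either reading. This is a biased counting rule as well as a missing definition.

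For assumed RNA detectability of 14 to 28 days, first-swab positives are about 10-17% of events if incidence is flat and about 1% if it doubles every 4 weeks. Pre-registration infections, before serologic removal, are 0-8% of events if incidence is flat, 0-30% if it halves every 4 weeks, and 0-0.5% if it doubles. The attack rate per person-week is about 8% too low only if entry is registration and the event count is held fixed. The documents do not support a single bias figure or a direction for the net effect.

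**What to change.** In Section 11.2:

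- Define entry for the primary analysis as the first evaluable nasal swab, and require that swab to be RNA-negative.
- Run the Kaplan-Meier curves and the person-week rates from that swab.
- Report RNA-positives at that swab as baseline prevalence, which the plan already intends to describe.
- Add a sensitivity analysis that counts them as events with time measured from registration.
- State how close to that swab the baseline blood must be for the seronegative restriction, and what the absence of a window for that blood means.
- State how children under 2, who give no blood, enter the analysis set.

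The cost is wording only, and no new data are needed. There will be somewhat fewer incident events and about two weeks less follow-up (22 rather than 24 weeks on the original schedule). Some infections truly acquired in Weeks 0-2 will move to the prevalence count, and the sensitivity analysis keeps them visible.

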11.3 Sample Size Calculations

Sample size considerations were based on the margin of error or precision. We plan to enroll and study 2000 index children representing 2000 family units. Power estimates were based on precision represented with width of the 95% confidence interval and using the Wilson interval (Software Stata version 16). Below are estimates for varying observed incidence of SARS-CoV-2 infection among these 2000 family units:

3%, the 95% confidence interval for the true incidence as 2.3% -- 3.84%;
5%, the 95% confidence interval for the true incidence as 4.1% -- 6.0%;
10%, the 95% confidence interval will be as 8.7% -- 11.4%
and 20% this confidence interval will be 18.3% - 21.8%.

12. Identification and Access to Source Data

12.1. Source Data

A source document is a document in which data are collected for the first time. In HEROS, the source documents are the electronic case report forms (eCRFs) completed by the participants in an online electronic data capture system hosted by Vanderbilt. Throughout the study, Vanderbilt will transfer deidentified HEROS data to the SACC where deidentified historic data imported from the index participant's parent study will be merged with the HEROS data and laboratory results and stored.

12.2. Access to Source Data

The site investigators and site staff are bound to maintain the strict confidentiality of medical and research information that may be linked to identified individuals.

12.3 Genomic Data Sharing Policy

DNA from participants in the HEROS study will be stored for analysis that will be limited to studies of SARS-CoV-2 infection. The NIH Genomic Data Sharing (GDS) policy requires deidentified genomic data from a NIH-funded study to be shared via dbGaP. However, GDS provides an exception to allow for controlled access to the data. The protocol chair for HEROS will submit a request for this exception which allows for deposition of summary (high level general) data with a 'controlled access guard' so that a future investigator would need to ask NIAID for permission to access the COVID-19 collected summary data and will be required to indicate that data analysis will be restricted to COVID-19 research.

13. Quality Assurance and Quality Control

The site principal investigator is required to keep accurate records to ensure that the conduct of the study is fully documented. The NIAID Division of Allergy, Immunology, and Transplantation (DAIT) is responsible for regular inspection of the conduct of the trial, for verifying adherence to the protocol, and for confirming the completeness, consistency,

and accuracy of all documented data. On a frequency determined by DAIT/NIAID, a clinical monitor from the SACCC will conduct a review of the conduct of the study by remote data review. Site study staff and participants will complete electronic case report forms and questionnaires online via a web-based electronic data capture system and data will be stored remotely at a central database. Data quality will be ensured through the electronic data capture system's continuous monitoring of data and real-time detection and correction of errors. All elements of data entry (e.g., time, date, verbatim text, and the name of the person performing the data entry) will be recorded in an electronic audit trail to allow all changes in the database to be monitored and maintained. In addition, SACCC data managers and statisticians will monitor data completeness and other elements of data quality throughout the trial and provide periodic reports on data quality.

14. Protocol Deviations

Since this is a Public Healthy Surveillance study and not human subject research, we will not be collecting protocol deviations. Missed samples and incomplete questionnaires are considered missing data.

15. Ethical Considerations

15.1. Informed Consent Process

The proposed prospective observational study fits the Public Health Surveillance exception at 45CFR46.102(l)(2). The exception allows for no IRB involvement since the study would not be considered human subject research and therefore not subject to the Common Rule. The informed consent is an information sheet about the study. The primary caregiver of the participant will read the information sheets and any questions will be addressed to the study investigators. If the caregiver wants to continue with the surveillance study and each member of the household that will take part in the study has reviewed and agrees with the requirements for participation in the information sheet, the caregiver will check "yes" and continue into the study web portal.

15.2 Privacy and Confidentiality

A participant's privacy and confidentiality will be respected throughout the study. It is possible that the study team may be required by law to share the surveillance data, including individually identifiable information, to a public health authority other than the National Institute of Health. The Human Health Services protection of human subjects regulations do not prevent investigators or institutions from fulfilling this requirement. The participants are informed that the results from the study will be confidential to the extent permitted by law.

16. Publication Policy

A publication policy of study results will be developed by the study investigators and the data coordinating centers prior to the completion of the study.
